#### 9. RESEARCH METHODS

## 9.1 Study design

We will take advantage of the unique nationwide register-data available to us, and construct country cohorts with individual-level information on dates of vaccination and dates of effectiveness end-points together with relevant covariate information. All Nordic residents are assigned a unique personal identifier at time of birth or immigration, enabling linkage between registers. The four Nordic

countries have universal and tax-financed healthcare systems and reporting to national registers is mandatory, providing near-complete follow-up of all residents over time. The cohort participants will be classified according to Covid-19 vaccinations received and followed up using survival analysis. We will utilize comparative designs avoiding comparisons with unvaccinated individuals. This will reduce concern about selection bias due to inherent differences in who chooses to remain unvaccinated.

The study period will start on 1 September 2022 in Denmark, 18 July 2022 in Finland, and 1 July 2022 in Norway and Sweden. These country-specific start dates correspond to when fourth dose vaccination was offered to the general public within the respective country. The study period will end on last date of data availability at time of analyses during autumn 2023 (tentative date: 30 September 2023).

The overall research design builds on target trial emulation methodologies to infer causal relative and absolute effect estimates according to average treatment effect among treated. Key components of the specification and emulation of the pragmatic target trials of the effectiveness of the bivalent Covid-19 booster vaccines against severe Covid-19 using Nordic nationwide registry data are including in table below.

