	Sweden	The Total Population Register. Defined as registered sex.		
	Denmark	The Danish Vaccination Register. Defined by the date where the respective vaccine dose examined was administered (i.e., third or fourth dose).		
Calendar time period of last	Finland	The National Vaccination Register. Defined by the date where the respective vaccine dose examined was administered (i.e., third or fourth dose).	Categorical (monthly [up to 33 levels]): 1 (27 December 2020-31 January 2021) to month 33 (September 2023)	
mutual vaccine dose a	Norway	The Norwegian Immunisation Register (SYSVAK).  Defined by the date where the respective vaccine dose examined was administered (i.e., third or fourth dose).		
	Sweden	The National Vaccination Register. Defined by the date where the respective vaccine dose examined was administered i.e., third or fourth dose).		
	Denmark	The Civil Registration System. Defined by last known address at the country-specific start date for the rollout of the fourth vaccine dose.		
Dogion of	Finland	The Finnish Population Information System. Defined by last known municipality of residence.	Categorical: Denmark, 5 levels;	
Region of residency	Norway	Norwegian Population Register. Defined by last known address at the country-specific start date for the rollout of the fourth vaccine dose.	Finland, 5 levels; Norway, 5 levels; Sweden, 9 levels	
	Sweden	The Total Population Register. Defined by last known address at the country-specific start date for the rollout of the fourth vaccine dose.		
Covid-19 vaccine priority groups b	Denmark	The Danish Vaccination Register. Defined as governmentally assigned Covid-19 vaccine priority groups, prioritised according to the risk of severe Covid-19 as well as whether being health and social care workers (last update 24 May 2021).	Categorical (3 levels): Severe Covid-19 risk group, healthcare personnel, others	

Variable	Country	Data source and details	Values/codes
	Finland	Register of Social Assistance. Severe Covid-19 risk group was defined as vulnerable individuals in 24-hours care (binary status per 27 December 2021).	
		Social and Healthcare Professionals Register. Healthcare personnel defined as individuals with the right to act as health care personnel as of 27 December 2021.	
	Norway	The Norwegian Information System for the Nursing and Care Sector. Severe Covid-19 risk group was defined as vulnerable individuals being residents at nursing homes (binary status per 27 December 2020).	

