		State register of employers and employees. Healthcare personnel defined as binary status per 27 December 2020.	
	Sweden	Register on persons in nursing homes. Severe Covid-19 risk group was defined as vulnerable individuals being residents at nursing homes (binary status as of 31 December 2020)	
	Sweden	The Longitudinal integrated database for health insurance and labour market studies. Healthcare personnel defined as healthcare worker occupation status as of 31 October 2018 (binary).	
	Denmark	The National Patient Register. Defined as primary diagnoses regardless of type of hospital contact registered before the start date for the country-specific rollout of the fourth vaccine dose (look-back 3 years).	Binary: yes/no (ICD-10 codes: J40- J47, J60-J67, J684, J701, J703, J841, J920, J961, J982, J983)
Comorbidity 1:	Finland	Care register for Health Care. Defined as primary or secondary diagnoses before 27 December 2020 (lookback 6 years).	Binary: yes/no (ICD-10 codes: J41- J44, J47)
pulmonary disease	Norway	Norwegian Patient Register. Defined as any recorded ICD-10 diagnosis during inpatient or outpatient contact in hospital or from private-practicing specialists and before first Covid-19 vaccination (look-back 3 years).	Binary: yes/no (ICD-10 codes: E84, J41-J47, J701, J703, J84, J98)
	Sweden	National Patient Register. Defined as any recorded ICD-10 diagnosis during inpatient or outpatient contact and before first Covid-19 vaccination (look-back 3 years).	Binary: yes/no (ICD-10 codes: E84, J41-J47, J84, J98)
Comorbidity 2: Cardiovascular conditions and diabetes	Denmark	The National Patient Register. Defined as primary diagnoses regardless of type of hospital contact registered before the start date for the country-specific rollout of the fourth vaccine dose (look-back 3 years).	Binary: yes/no (ICD-10 codes: E10- E11, I110, I130, I132, I20-I23, I420, I426-I429, I48, I500-I503, I508, I509)
	Finland	Care register for Health Care, Register of Primary Health Care Visits, Special Reimbursement Register and Prescription Centre database. Defined as primary or secondary diagnoses (look-back 6 years) or drug	Binary: yes/no (ICD-10 codes: E10, E11, E13-E14, I11-I13, I15, I20- I25; ICPC-2 codes: T89, T90; ATC codes: A10A, A10B)

Variable Country		Data source and details	Values/codes	
		prescriptions (look-back 3 years) before 27 December 2020.		

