#### 9.4 Data sources

All data sources are nationwide registers in native format. All study subcontractors have access to their country-specific data and can link data between registers for the purpose of our study. Given the no-to-very-little lag time of the data source, our analyses will be reflecting real-time information. We will have full data availability for all variables (with no missing data; all the exposures, outcomes, or covariates are either present or not) during the study period and as reporting to national registers is mandatory/structurally implemented, this provides a near-complete follow-up of all residents over time.

Country/data source	Details
Denmark	
The Civil Registration System (14)	The register provides the unique personal identifier for all permanent residents of Denmark that allows linkage between all Danish health care registers and civil registrations systems. In addition, it holds general demographic information such as birthdate and sex as well as continuously updated information and dates on historical addresses, immigration and emigration status, and death.
The Danish Vaccination Register (15)	The register holds information on all vaccinations administered in Denmark including vaccination date, type/trade name, dose, and product batch number ever since Nov 15, 2015 (where reporting to the register became mandatory). Specifically related to this study, the Danish Health Agency have provided the governmentally assigned Covid-19 vaccine priority groups that were prioritised groups according to the risk of severe infection as well as whether being health and social care workers.
The Danish Microbiology Database (16)	Information on positive PCR tests for SARS-CoV-2 are obtainable via The Danish Microbiology Database (MiBa) that has data on all microbiology samples analysed at Danish microbiology departments as well as test results, date of sampling, date of analysis, type of test, and interpretation of test. The SARS-CoV-2 PCR tests are freely available to all individuals in Denmark regardless of symptoms status.
The National Patient Register (17)	The register holds information on all hospital contacts in Denmark including the duration of the contact, and diagnoses, which are assigned by the treating physician and registered according to ICD-10 classification system (since 1994).
Finland	

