## 9.7 Data analysis

#### **Procedures**

[figure not shown]
We will use a matched study design to evaluate the effectiveness of a bivalent BA.1 or BA.4-5 (or monovalent [original]) mRNA-booster vaccine (as the fourth dose) in comparison with having received three monovalent vaccine doses only (i.e., nonboosted with a fourth dose) as well as between fourth dose recipients. For the boosted vs nonboosted (i.e., 4 vs 3 dose) comparisons, individuals who have received a fourth dose will be matched on the day of vaccination with individuals who have not yet received a fourth dose. Individuals will be matched on age (5-year bins), calendar time according to when the third dose was received (monthly bins), and a propensity score including sex, region of residence, vaccination priority groups (i.e., individuals at high-risk of severe Covid-19 or healthcare workers), selected comorbidities (chronic pulmonary disease, cardiovascular conditions or diabetes, autoimmunity-related conditions, cancer, and moderate to severe renal disease), and previous history of SARS-CoV-2 infection characteristics. The day the fourth dose was administered within each matched pair will serve as the index date for both individuals. If individuals who were included as a

matched nonboosted (previously three-dose vaccinated) individual (i.e., a reference individual) received a fourth dose later than the assigned index date, they will be allowed to potentially re-enter as a fourth-dose recipient in a new matched pair on that given date. The figure below illustrates the study cohort construction.

For the between booster (i.e., 4 vs 4 dose) comparison, BA.4-5 booster and BA.1 booster recipients (as a fourth dose) will be matched on age (5-year bins), calendar time according to when the fourth dose was received (monthly bins), and a propensity score including sex, region of residence, vaccination priority groups (i.e., individuals at high-risk of severe Covid-19 or healthcare workers), selected comorbidities (chronic pulmonary disease, cardiovascular conditions or diabetes, autoimmunity-related conditions, cancer, and moderate to severe renal disease), and previous history of SARS-CoV-2

infection. The day the fourth dose was administered will serve as the index date for each respective individual. The figure below illustrates the study cohort construction.

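### Care-status and comorbidity covariates in Finland, Norway and Sweden predate the study start by up to about 1.6 years, so balance in current frailty and morbidity at the fourth dose is not assured

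*Protocol*

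**What the plan says.** Section 9.1 sets the start of the study: "The study period will start on 1 September 2022 in Denmark, 18 July 2022 in Finland, and 1 July 2022 in Norway and Sweden". Section 9.7 (Procedures) sets baseline for the 4 vs 3 dose comparison: "The day the fourth dose was administered within each matched pair will serve as the index date for both individuals". The target-trial table in 9.1 treats assignment as random once individuals are matched on baseline covariates.

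The Covariates table in 9.3 dates those covariates as follows.

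- **Finland.** The severe-risk group is "vulnerable individuals in 24-hours care (binary status per 27 December 2021"), and healthcare-personnel status has the same date. Comorbidities stop a year earlier, for example in pulmonary disease: "Defined as primary or secondary diagnoses before 27 December 2020 (lookback 6 years").
- **Norway.** "Severe Covid-19 risk group was defined as vulnerable individuals being residents at nursing homes (binary status per 27 December 2020"). Healthcare-personnel status has the same date. Comorbidities are those recorded before the person's first Covid-19 vaccination.
- **Sweden.** Nursing-home status is taken at 31 December 2020 and antidiabetic drug use from 2020. Comorbidities stop at first Covid-19 vaccination. For occupation: "Healthcare personnel defined as healthcare worker occupation status as of 31 October 2018 (binary").
- **Denmark.** Comorbidities run to the start of the fourth-dose rollout. The priority group was last updated on 24 May 2021.

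Two other definitions use later dates in every country. Prior SARS-CoV-2 infection is taken up to the fourth-dose rollout (9.3), and the diagnosis-based immunocompromised conditions are taken within 3 years before the index date (9.2). Section 9.4 adds: "Given the no-to-very-little lag time of the data source, our analyses will be reflecting real-time information".

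**The concern.** The design relies on matched pairs being alike at the day of the fourth dose. Under these definitions, a cancer, heart failure or renal diagnosis, or a move into a nursing home, that falls between the covariate date and the index date is coded as absent. If such changes affect both whether a person takes the fourth dose and the risk of severe Covid-19 or death, part of that confounding stays in the matched estimate.

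The 4 vs 3 dose comparison is the most exposed. Section 9.9 says that near day 365, the primary time point, its reference group is dominated by people who never take a fourth dose, and that healthy-vaccinee bias follows if the included covariates do not capture how they differ. Objective #3 reuses the same covariates, apart from prior infection and with length of stay added, for mortality after discharge. Its baseline is later still, so the covariates are older.

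The checks planned in 9.8 do not reach this. Matching diagnostics assess the recorded, older values. The delayed start of follow-up at day 21/28 is aimed at transient effects around vaccination and at infections before the index date.

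**Working it through.** The protocol states no figure for covariate age, so there is none to reproduce.

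**1. Age of each covariate.** Inputs: covariate dates from the table in 9.3; start dates from 9.1; end of study from 9.1 ("tentative date: 30 September 2023"). Formula: gap = reference date − covariate date; years = days / 365.25.

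| Covariate | Date | Gap to country start | Gap to 30 Sep 2023 |
|---|---|---|---|
| Finland, 24-hour care and healthcare personnel | 27 Dec 2021 | 203 d (0.56 y) | 1.76 y |
| Finland, comorbidities | 27 Dec 2020 | 568 d (1.56 y) | 2.76 y |
| Norway, nursing home and healthcare personnel | 27 Dec 2020 | 551 d (1.51 y) | 2.76 y |
| Sweden, nursing home and antidiabetic drugs (end of 2020) | 31 Dec 2020 | 547 d (1.50 y) | 2.75 y |
| Sweden, healthcare personnel | 31 Oct 2018 | 1,339 d (3.67 y) | 4.91 y |
| Denmark, priority group | 24 May 2021 | 465 d (1.27 y) | 2.35 y |

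The last column is an upper limit, because index dates fall between the start and the end of the study period.

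Norwegian and Swedish comorbidities have no common date. Vaccination began on 27 December 2020 (9.3, Exposures), so the gap to 1 July 2022 is at most 551 days (1.51 y). For assumed first doses on 1 June 2021 and 31 December 2021 it is 1.08 y and 0.50 y.

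For fixed-date markers of frailty or morbidity in the three countries, the range at study start is therefore 0.56 to 1.56 years.

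**2. Is there a stated reason for the dates?** The footnote to the table explains why diagnosis codes differ by country (national experts, registration practice). It does not explain why the dates differ. The immunocompromised definition already needs recent diagnoses from all four countries.

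**3. What an outdated marker could do.** Every input here is assumed; none is in the documents. Let current frailty be present in 5% of boosted (p_b) and 10% of nonboosted (p_u), with risk ratio R for the outcome and no true vaccine effect.

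- Without matching on frailty, the spurious ratio is [1 + p_b(R−1)] / [1 + p_u(R−1)]. R = 3 gives 1.10/1.20 = 0.917; R = 5 gives 1.20/1.40 = 0.857.
- Now match exactly on an old marker with sensitivity 50% and specificity 98%, and take R = 5. Among boosted, 4.4% are marker-positive (0.025 + 0.019). Current frailty in marker-positives is 0.025/0.044 = 0.568 (boosted) and 0.050/0.068 = 0.735 (nonboosted). In marker-negatives it is 0.025/0.956 = 0.0262 and 0.050/0.932 = 0.0536. Standardised to the boosted, the numerator is 1 + 4 × 0.05 = 1.200. The denominator is 0.044(1 + 4 × 0.735) + 0.956(1 + 4 × 0.0536) = 1.335. The ratio is 0.899.
- The same calculation over R = 3 to 5 gives 0.942 to 0.899 at sensitivity 50%, and 0.958 to 0.926 at 70%.
- A factor of 0.90 turns a true VE of 20% into 1 − 0.90 × 0.80 = 28%. It turns 67.8%, the earlier Nordic BA.4-5 estimate cited in section 7, into 1 − 0.90 × 0.322 = 71.0%.
- Reverse the imbalance (10% boosted, 5% nonboosted) at sensitivity 50% and R = 5. The numerator is 1.400 and the denominator 0.068(1 + 4 × 0.568) + 0.932(1 + 4 × 0.0262) = 1.252. The ratio is 1.118, and a true VE of 20% appears as 1 − 1.118 × 0.80 = 10.6%.

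**The case against.** A reader might infer from the dates that matching fails to balance frailty and morbidity, with covariates up to 3.7 years old. The documents do not support that.

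- The 3.7 years belongs to Swedish healthcare occupation alone, which measures neither frailty nor morbidity.
- Norwegian and Swedish comorbidity dates follow each person's first vaccination, so they are not frozen at a calendar date.
- Matching also uses 5-year age bins and month of third dose, and prior infection runs to rollout. People given a fourth dose before the country start are excluded as likely vulnerable (9.2). In Finland, Norway and Sweden, vulnerable elderly people and nursing-home residents were offered that dose from spring 2022, so the exclusion removes many of those who became frail after the covariate date. It does not remove those who declined or missed that dose, and they are potential nonboosted comparators.
- For 4 vs 4 dose comparisons, 9.9 describes the type of booster as given without selection, so the concern is much weaker there.
- Denmark is only a partial model: its comorbidities are current, but its priority group is older at study start than Finnish care status.
- Section 9.9 already acknowledges residual confounding and healthy-vaccinee bias. It does so in general terms and does not mention covariate dates.

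These points limit the claim. They do not explain why available diagnoses are left out of the matching.

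**Conclusion.** The concern stands in a limited form. In Finland, Norway and Sweden, care status and comorbidity with fixed dates are 0.56 to 1.56 years old at study start and older at later index dates. Person-specific comorbidity in Norway and Sweden adds gaps of at most about 1.5 years. The Danish priority group shares the problem at 1.27 years. Balance in current frailty and morbidity at the index date is therefore not assured in the 4 vs 3 dose comparison and in objective #3, and the planned diagnostics cannot show whether it holds.

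The documents do not show that imbalance exists, how large a bias would be, or which way it would run. The illustrative factors rest wholly on assumed prevalences, risk ratios and marker accuracy. They show only that a given factor moves a low VE by more percentage points than a high one, which matters for late-interval and waning estimates if VE has fallen by then. The point merits a change to the plan because recent diagnoses are already required for the immunocompromised cohort.

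**What to change.** 1. In Finland, Norway and Sweden, measure comorbidity diagnoses and prescriptions up to the country-specific start date, as Denmark does for comorbidities, or preferably up to each index date, as the immunocompromised definition does. Keep each country's codes and look-back length; harmonising those is a separate question.
2. In all four countries, update care-status, priority-group and occupation variables to the latest register date before baseline.
3. Where a register has no newer data, say so for that variable in section 9.9. The general statement in 9.4 about data lag does not establish that every occupation or care register is current.
4. Keep the present definitions as a sensitivity analysis, so that the effect of the older dates can be seen.

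The cost is some additional data extraction and programming. For comorbidity diagnoses it should be small, since recent diagnosis records are needed in any case. The occupation and care registers may take more work or prove impossible to update.

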Length of Covid-19 hospitalisation	Finland	National Care Register for Health Care and the National Infectious Diseases Register. Time between admission and final discharge date.	Categorical (adjustment variable	
	Norway	The Norwegian Intensive Care and Pandemic Registry (NIPaR). Time between admission and final discharge date.	for objective #3 only; 4 levels)e: ≤2 days, 3-5 days, 6-14 days, >14 days	
	Sweden	The Swedish Patient Register and the Register on surveillance of notifiable communicable diseases (SmiNet). Time between admission and final discharge date.		

<sup>a Due to data availability in Sweden, the country-specific end of study period might be some weeks earlier. For the bivalent 4 dose vs monovalent 4 dose comparisons, we will consider whether alternative time period bins should be used for these analyses to optimize the balance between covariate control and matched cohort size. b To account for the risk of severe Covid-19, we will adjust for targeted Covid-19 high-risk groups of severe Covid-19, specifically established for each country. In Denmark, the Covid-19 vaccine priority groups were governmentally assigned and individuals were prioritised according to the risk of severe infection (identified by the treating physicians) as well as whether being health or social care workers. In the remaining countries, the variable was constructed based on the identification of vulnerable individuals (as defined by those receiving nursing care or living in nursing homes) and whether being health or social care workers. c Autoimmunity-related conditions includes a range disorders such as inflammatory bowel diseases, diseases involving the blood, immune mechanism or endocrine systems, inflammatory rheumatic diseases, psoriasis, lupus erythematosus, multiple sclerosis; subject to country-specific definitions. The selected diagnosis codes to define comorbidities were country-specific, based on inputs from national experts and country-specific registration practices as part of the general national surveillance purposes. This was done as we anticipated that

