Finnish Population Information System (18)	The register is held by the Digital and Population Data Services Agency and contains personal data on all permanent residents in Finland such as the unique personal identifier, date of birth, place of residence, date of death, and date of immigration, and emigration.
Register of Social Assistance (19)	The register is held by the Finnish Institute for Health and Welfare and contains information on individuals receiving long-term care and/or social assistance (in e.g., nursing homes, people's own homes or other institutions) including social rehabilitation.

Country/data source	Details
Social and Healthcare Professionals Register (20)	The register holds data on individuals right to act as health care personnel.
National Vaccination Register (21)	The register is based on the Register of Primary Health Care Visits and contains information on all Covid-19 vaccinations administered in Finland including date of vaccination, batch number, and trade name.
National Infectious Diseases Register (22)	The register is held by the Finnish Institute for Health and Welfare and contains information on notifiable diseases in accordance with the Finnish Communicable Diseases Act that must be reported by the laboratories and the treating-physicians, or the physician performing an autopsy and hold information on sample dates of all laboratory-confirmed SARS-CoV-2 infections in Finland
National Care Register for Health Care (23)	The register is held by the Finnish Institute for Health and Welfare and comprises information on all inpatient and outpatient hospital contacts in Finland, including admission and discharge dates, whether hospitalisation was planned or acute, codes for discharge diagnoses (according to ICD-10) and surgical procedures, and whether discharged as deceased, to own private residence or other health care facilities.
Special Reimbursement Register and Prescription Centre database	These databases are maintained by the Finnish Social Insurance Institution. The Special Reimbursement Register holds information on individuals entitled to special reimbursement for medical expenses. The Prescription Centre database holds information on individuals using selected medications of interest.
Register of Primary Health Care Visits (24)	The register is held by Finnish Institute for Health and Welfare and holds data on all primary health care services delivered in Finland.
Norway	

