The Emergency Preparedness Register for Covid-19 (25) (consisting of the data sources below)	Data for the Norwegian analyses were collected through the Emergency preparedness register for Covid-19 ("Beredt C19"), which is administered by the Norwegian Institute of Public Health, according to the Norwegian Health Preparedness Act §2-4. The register was established in 2020 to provide authorities with up-to-date information on prevalence, causal relationships, and consequences of the Covid-19 epidemic in Norway and captures the entire population. The register includes information from the healthcare system and the national health registers presented below.
Norwegian Population Register	The register holds information on birthdate, immigration, emigration status, and death for all residents of Norway.
State register of employers and employees (NAV AA register) (26)	The register holds lists of all employment relationships in Norway for which employers and contractors are obliged to report to. Employees are classified according to the Norwegian Standard Classification of Occupations which we then used to identify whether individuals were health care personnel.
The Norwegian Information System for the Nursing and Care Sector (IPLOS) (27)	The register contains information on the health care services provided by municipalities and reporting of applicants and recipients of such services is mandatory in Norway. Available data includes information on home care services and out-of-hospital institutional care, including nursing home stays.
The Norwegian Immunisation Register (SYSVAK) (28)	The register holds information on administered vaccines in through the Norwegian vaccination programme, including date of administration and type of vaccine/trade name. For the Covid-19 vaccines, reporting to the register is mandatory.

Country/data source	Details
Norwegian Surveillance System for Communicable Diseases (MSIS)	The register holds information on selected infectious diseases for which reporting to the register is mandatory, including all Covid-19 tests and testing date and results.
The Norwegian Patient Registry (NPR) (29)	The register holds data on all contacts with specialist health-care services in Norway, including admission and discharge dates diagnoses recorded according to ICD-10 during hospitalisation or outpatient contact.

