The Norwegian Intensive Care and Pandemic Registry (NIPaR) (30)	This is a national clinical registry that was expanded to include Covid-19 patients in conjunction with the Covid-19 pandemic. The register holds information on all patients who have tested positive for SARS-CoV-2 and were admitted to hospital including intensive care unit admissions. It is mandatory for all Norwegian hospitals to report to this register.
Sweden	
The Total Population Register (31)	The register is held by Statistics Sweden and contains data on the unique personal identifier assigned to all individuals in Sweden plus general demographic information such as date of birth, sex, country of birth, place of residence, and date of immigration and emigration.
The Cause of Death Register (32)	The register holds information on date of death and underlying as well as contributing causes of death.
The Longitudinal Integrated Database For Health Insurance And Labour Market Studies (LISA) (33)	The database is held by Statistics Sweden and holds many socioeconomic variables such as data on occupation which we used to identify whether individuals were health care personnel.
Register On Persons In Nursing Homes (34)	The register is held by the National Board of Health and Welfare and holds data on nursing care given in either nursing homes, own homes or other institutions to elderly and/or persons with physical, psychiatric or intellectual disabilities.
The National Vaccination Register (35)	The register is held by the Public Health Agency of Sweden and contains information on administered Covid-19 vaccines in Sweden including data on date of administration, the specific vaccine products, substance, formulation, batch number and dose number (for repeated doses).
Register On Surveillance Of Notifiable Communicable Diseases (Sminet) (36)	The register is held by the Public Health Agency of Sweden and contains information on notifiable diseases (for which reporting is mandatory) reported by either the analysis performing laboratories, the treating physician or autopsy performing physician, in accordance with the Swedish Communicable Diseases Act. Data included are e.g., date of disease occurrence, date of testing, date of positive test, and diagnoses.

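### The severe-risk covariate stops at nursing-home residence (Norway, Sweden) or 24-hour care (Finland) although the named registers also record care at home, which leaves residual confounding by frailty

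*Protocol*

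**What the plan says.** The covariate table in protocol section 9.3 gives the priority-group variable three levels: severe-risk group, healthcare personnel, others. Outside Denmark the severe-risk level is defined as follows.

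- Norway: "Severe Covid-19 risk group was defined as vulnerable individuals being residents at nursing homes", with status fixed at 27 December 2020.
- Sweden: the same wording, with status fixed at 31 December 2020.
- Finland: "Severe Covid-19 risk group was defined as vulnerable individuals in 24-hours care (binary status per 27 December 2021"). The row does not say where the care is given.

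Two other places in section 9.3 describe the group. Footnote b, speaking of the countries other than Denmark, identifies vulnerable individuals "as defined by those receiving nursing care or living in nursing homes". The opening Covariates paragraph lists nursing-home residents, healthcare personnel and people at risk because of comorbidities.

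Section 9.4 describes the registers named for the variable.

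- Norway (IPLOS): "Available data includes information on home care services and out-of-hospital institutional care, including nursing home stays".
- Sweden: the register "holds data on nursing care given in either nursing homes, own homes or other institutions".
- Finland: the register "contains information on individuals receiving long-term care and/or social assistance", and the entry goes on to name people's own homes among the places of care.

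In Denmark, by contrast, the level rests on risk identified by treating physicians (footnote b).

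**The concern.** Under the table as written, someone in Norway or Sweden who depends on home care, and is not healthcare personnel, is coded as others, alongside fully independent people. In Finland the same holds for home care short of 24 hours a day. Home-care receipt marks functional dependency, and the registers already named for this variable hold it.

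What is at stake is the 4 vs 3 comparison. Section 9.9 states that towards day 365 the comparator is dominated by people who never take a fourth dose, and that healthy vaccinee bias can follow if the covariates do not capture how they differ. Day 365 is the time point of primary objective #1. Objective #3 is also exposed: it models all-cause death after discharge with largely the same covariates, and dependency plausibly predicts that outcome strongly.

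The three descriptions of the group also leave a programmer unsure which group to code.

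**Working it through.** **Step 1: what reaches people living at home.** Section 9.7 matches the 4 vs 3 pairs on 5-year age bin and third-dose month, and on a propensity score with sex, region, priority group, five comorbidity groups (pulmonary; cardiovascular or diabetes; autoimmune; cancer; renal) and infection history. Objective #3 uses a Cox model with the same covariates, minus previous infection and plus length of stay. The comorbidity code lists for these countries do not cover dementia or stroke, and no listed covariate measures home care or functional dependency.

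**Step 2: age of the flag.** From 27 December 2020 (Norway) or 31 December 2020 (Sweden) to the start on 1 July 2022 is just over 18 months. From 27 December 2021 to 18 July 2022 (Finland) is nearly 7 months. People who became dependent in between are not flagged.

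**Step 3: possible size.** The protocol gives no figure for this covariate, so there is none to reproduce. For one binary unmeasured confounder with prevalence p1 in boosted and p0 in unboosted after matching, and risk ratio R for the outcome:

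b = [1 + p1(R - 1)] / [1 + p0(R - 1)], and RR_observed = RR_true × b.

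The only inputs from the protocol are the VEs of 67.8% (BA.4-5) and 65.8% (BA.1) against hospitalisation that section 7 cites from the earlier Nordic study. **All p1, p0 and R below are assumptions.** Corrected VE = 1 - (1 - VE_observed)/b.

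| R | p1 | p0 | b | 67.8% becomes | 65.8% becomes |
|---|---|---|---|---|---|
| 2 | 5% | 6% | 0.991 | 67.5% | 65.5% |
| 3 | 5% | 8% | 0.948 | 66.0% | 63.9% |
| 5 | 5% | 10% | 0.857 | 62.4% | 60.1% |
| 2 | 8% | 5% | 1.029 | 68.7% | 66.8% |
| 3 | 10% | 5% | 1.091 | 70.5% | 68.7% |
| 5 | 10% | 5% | 1.167 | 72.4% | 70.7% |

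For example, b = 1.20/1.40 = 0.857 and 1 - 0.342/0.857 = 60.1%. The shifts run from 0.3 points (67.8 to 67.5) to 5.7 points (65.8 to 60.1). The sign depends on which arm holds more home-care recipients.

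**Step 4: low VE, and death.** Since VE_observed - VE_true = (1 - VE_true)(1 - b), the same b moves a low VE more. If the booster had no effect, the spurious VE is 1 - b. These cases assume more home care among the unboosted:

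| Outcome | R | p1 | p0 | b | Spurious VE |
|---|---|---|---|---|---|
| Hospitalisation | 3 | 6% | 8% | 1.12/1.16 = 0.966 | 3.4% |
| Hospitalisation | 3.5 | 6% | 9% | 1.150/1.225 = 0.939 | 6.1% |
| Hospitalisation | 4 | 6% | 10% | 1.18/1.30 = 0.908 | 9.2% |
| Covid-19 death | 5 | 6% | 8% | 1.24/1.32 = 0.939 | 6.1% |
| Covid-19 death | 7 | 6% | 9% | 1.36/1.54 = 0.883 | 11.7% |
| Covid-19 death | 8 | 6% | 10% | 1.42/1.70 = 0.835 | 16.5% |

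With the outer hospitalisation factors, a true VE of 30% would appear as 1 - 0.7 × 0.966 = 32.4% to 1 - 0.7 × 0.908 = 36.5%. At a true VE of 65.8-67.8% the same factors shift it by only about 1 to 3 points (0.322 × 0.034 = 1.1 points; 0.342 × 0.092 = 3.1 points).

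**The case against.** Several points on the other side stand.

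- A reader might infer that frail people at home are unadjusted. They are not: age, third-dose month, sex, region, five comorbidity groups and infection history are all handled. What remains is frailty beyond those variables.
- A reader might infer that all three countries count only institutional residents. The Norwegian and Swedish rows say nursing homes. Finland's says 24-hour care, and its register covers own homes as well as institutions.
- A reader might infer that footnote b flatly contradicts the table. It can be read as a pooled summary, with nursing care standing for Finland and nursing homes for Norway and Sweden, and it never mentions home care. The comorbidity wording in the opening paragraph can likewise be read as a list across countries. The mismatch is one of wording, but it leaves the coding open.
- A reader might infer that excluding early fourth doses (section 9.2, criterion 5) has nearly emptied the flagged group. Section 9.3 says the spring 2022 rollout in these countries targeted both nursing-home residents and the vulnerable elderly. The exclusion therefore also removes some frail people outside nursing homes, and the protocol counts neither group.
- Sections 9.7 and 9.9 do not ignore the problem. Residual confounding and healthy vaccinee bias are acknowledged, and section 9.8 adds a start at day 21/28. That analysis addresses early, transient effects, not lasting differences in frailty. For comparisons between boosters, section 9.9 describes the type received as unselective, so the point does not carry over readily.
- Home-care status taken at the present end-2020 dates would itself be stale. This is right, and the fix must include a later date.

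Acknowledging a bias in general terms is not a reason to leave out a marker that the named registers already hold.

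**Conclusion.** The covariate is narrower than its data sources allow. Home-care dependency is not adjusted for in Norway and Sweden, nor in Finland where the care falls short of 24 hours. Residual confounding by frailty therefore remains in the 4 vs 3 comparison and in objective #3, in addition to what the existing covariates remove.

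Its size is not given in the documents. On the assumed inputs it is about 0 to 6 percentage points at a VE of 66-68%. It is larger where true VE is low, which includes late intervals if protection wanes (objective #2), or where the outcome is death. These figures apply to each affected country's estimate; the pooled estimate also includes Denmark, where the level is defined differently.

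A reader might infer that VE is bound to be overstated, since section 9.9 speaks of healthy vaccinee bias. The documents do not establish that: they give no home-care prevalence by arm, and the reverse imbalance would understate VE. Nor do they support any single figure for the bias.

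**What to change.** In Finland, Norway and Sweden, split the severe-risk level in two: (i) nursing home or 24-hour care, and (ii) home care or home nursing, taken from the same register. Take status as close to the country-specific start date as each register allows.

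Use both levels in the 4 vs 3 propensity score and in the objective #3 Cox model. If they are not adopted for the main analysis, prespecify a sensitivity analysis that includes them.

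Make the covariate table, footnote b and the opening Covariates paragraph state one definition per country, and say whether Finland's 24-hour care includes care given at home.

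The cost is a little more extraction from registers already listed, one extra covariate level in three countries, and possibly slightly fewer matched pairs. Design and outcomes do not change.
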